14.4 Secondary Objectives

There are several planned secondary analyses. Selected non-hematologic and hematologic toxicities will be described, as measured by the NCI Common Toxicity Criteria, version 4.0, with the maximum grade over all cycles used as the summary measure per patient.

In order to estimate the efficacy of BYL719 plus letrozole or exemestane, we will calculate the following for each arm, Arm C and Arm D separately in the expansion cohort only:

- a. Progression-free survival (PFS) will be examined using Kaplan-Meier methods.
- b. Overall response rate (ORR = complete response (CR) plus partial response (PR)) will be calculated with an exact confidence interval.
- c. Clinical benefit rate (CBR = CR + PR + stable disease at 16 weeks) will be calculated with an exact confidence interval.
- d. Time to treatment failure (TTF) will be examined using Kaplan-Meier methods.

Pharmacokinetic parameters such as AUC and C_{max} of daily BYL719 will be calculated.

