3.8 Hypothesis

We therefore propose a clinical trial of BYL719 in combination with an AI. We hypothesize that the combination of BYL719 with an AI will represent a highly potent, non-chemotherapy combination that safely, effectively and durably treats HR+ breast cancers. We additionally hypothesize that intermittent dosing of BYL719 will allow for dose escalation and treatment with less toxicity than daily BYL719.

Hyperglycemia is the most common side effect of BYL719, and may even represent a pharmacodynamic marker of clinical efficacy. Significant overlapping toxicity between BYL719 and either letrozole or exemestane is not anticipated. However, these drugs have not been tested together in humans. Therefore, we propose a phase I trial of this combination to evaluate the safety and tolerability of this regimen. The starting dose of BYL719 on Arms A and B of this study (300mg daily) will be 75% of the single-agent MTD (400mg daily). As of January 2014, we are closing accrual to Arms A and B and amending the study to allow for examination of intermittent dosing through the addition of Arms C and D to the trial. The starting dose of BYL719 on Arms C and D of this study will be 250mg, with intermittent dosing schedules as outlined above. Once a safe dose of BYL719 in the combination has been established for Arms C and D, we propose an expansion phase for these arms to further evaluate safety, and to estimate the efficacy of this combination.

We propose testing BYL719 in an unselected population in regards to *PIK3CA* genotype. Preclinical data suggest that subsets of tumors with alterations in the PI3K pathway may be particularly sensitive (e.g., *PIK3CA* mutation) or resistant (e.g., PTEN loss) to this combination. This has yet to be evaluated clinically. It is not clear that the presence or absence of a *PIK3CA* mutation restricts the efficacy of BYL719 in patients with HR+ breast cancer which has progressed on endocrine therapy. The BOLERO-2 study showed efficacy of mTOR inhibition in an unselected population in regards to *PIK3CA* genotype, and no biomarker data is available.⁷ We therefore propose testing BYL719 in an unselected population in regards to *PIK3CA* genotype, and a detailed molecular analysis of tumor biopsies of patients on this trial, looking at next generation sequencing and fine copy number

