9.5 Dose-Finding Phase

The dose-finding phase will follow a standard 3 + 3 design. A treatment cycle will consist of 28 days. Patients will continue on treatment until progression of disease or unacceptable toxicity.

For Arms A and B, the starting dose of BYL719 for the first cohort (Cohort 0) will be 300mg daily, which is 75% of the MTD from the phase I study. Treatment doses for BYL719 for each cohort are presented below:

Table 9-3 Dose-Finding Cohorts for Arms A and B

COHORT	BYL719 dose
+2	400mg orally once daily (100% of MTD for single agent BYL719)
+1	350mg orally once daily (87.5% of MTD for single agent BYL719)
0 (starting dose)	300mg orally once daily (75% of MTD for single agent BYL719)
-1	250mg orally once daily (62.5% of MTD for single agent BYL719)
-2	200mg orally once daily (50% of MTD for single agent BYL719)

For Arms C and D, the starting dose of BYL719 for the first cohort (Cohort 0) will be 250mg daily. Treatment doses for BYL719 for each cohort on Arms C and D are shown below:

Table 9-4 Dose-Finding Cohorts for Arms C and D

COHORT	BYL719 dose
+2	350mg
+1	300mg
0 (starting dose)	250mg
-1	200mg

During the dose-finding phase, a periodic teleconference will be held at least monthly with the primary investigator and Novartis to review toxicity data and ensure patient safety moving forward.

Dose escalation or de-escalation schema:

On each arm, three patients will be enrolled onto Cohort 0 at the starting BYL719 dose. All patients within a cohort will be observed for toxicity for one cycle (28 days) prior to entering additional patients. If a patient discontinues study participation during the first cycle (within 28 days of starting study treatment) for reasons unrelated to an adverse event, an additional patient may be enrolled to replace that subject. Between 6 and 15 patients in each arm will be necessary to determine the recommended phase II dose of BYL719 in combination with letrozole or exemestane.

There will be no inpatient dose escalation. Inpatient dose reductions of BYL719 will not be allowed during Cycle 1 (within 28 days of starting study treatment), unless a DLT has occurred and been counted towards informing enrollment of future cohorts of patients. This is in order to accurately determine the safe and tolerable dose of BYL719 when used in combination with letrozole or exemestane.

Schema for Cohort 0:

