	
days of last dose of BYL719), although a 2 week window is allowed.
 
c Companion normal DNA for targeted gene sequencing analysis (1ml whole blood for correlative science, Section 10.12)
 
d Day 1 +/- 7 days of Cycle 3, Cycle 5, and then every 3rd cycle (Cycle 8, Cycle 11, etc)
 
e If EOD not already performed in the last 28 days
 
f Cycle 3, Cycle 4, Cycle 5, Cycle 6, Cycle 8 and Cycle 10 for letrozole arm (Arm A) and Cycle 3 only for exemestane arm (Arm B)
 
g Estradiol to be tested only on women who are receiving pharmacologic ovarian suppression
 
h Patients on study under Amendment 13 will have relevant blood and cfDNA collection every other cycle (+/- 7 days).
 
i Patients on study under Amendment 13 will have EOD evaluations will be preformed every 16 weeks +/- 4 weeks from their last scan.
 
j Patients on study under Amendment 13 will have EKG evaluations every 4 cycles. EKG evaluations may be preformed more frequently at the discretion of the MD.

--	---

10.2 Cycle 1 Day 1

- 10.2.1 MD visit, with history and physical examination, including weight, blood pressure, pulse, ECOG performance status, and updated medication list. Concurrent medications will be reviewed for potential drug-drug interactions with study medication (see Section 9.6).
- 10.2.2 Toxicity will be assessed and the type, severity, timing, and relationship of each adverse event to therapy will be determined as per the NCI Common Toxicity Criteria, version 4.0.
- 10.2.3 Fasting bloodwork prior to taking BYL719 in clinic on this day (if screening bloodwork was not performed within 72 hours of dosing). A light breakfast may be consumed after fasting plasma glucose draw. BYL719 may be administered 1 hour after breakfast. Patients should fast for 1 hour after the administration of BYL719. Bloodwork results do not need to be resulted prior to dosing on this day; however, all bloodwork must be reviewed and the patient contacted within 24 hours (excluding weekends and holidays) if an abnormality is detected which would affect dosing. If a patient is being screened and starting treatment on the same day, then results of CBC, CMP and fasting glucose must be reviewed prior to enrollment and initiation of treatment.
- CBC, including WBC (differential not required), Hgb and platelet count
 - CMP, including BUN, creatinine and liver function tests
 - Magnesium, amylase and lipase
 - Fasting glucose
 - PT/INR and PTT

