10.3 Cycle 1 Day 8 (+/- 3 days)

10.3.1 MD visit, with history and physical examination, including weight, blood pressure, pulse, ECOG performance status, and updated medication list. Concurrent medications will be reviewed for potential drug-drug interactions with study medication (see Section 9.6).

10.3.2 Research blood draw for plasma collection from 10ml blood for cfDNA extraction and analysis

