10.7 Subsequent Cycles (Cycle 3+) Day 1 (+/- 7 days)

10.7.1 One MD clinic visit per cycle, with history and physical examination, including weight, blood pressure, pulse, ECOG performance status, patient drug diary review, and updated medication list. Concurrent medications will be reviewed for potential drug-drug interactions with study medication (see Section 9.6).

10.7.2 Toxicity will be assessed and the type, severity, timing, and relationship of each adverse event to therapy will be determined as per the NCI Common Toxicity Criteria, version 4.0.

10.7.3 Fasting bloodwork prior to taking BYL719 in clinic on this day. A light breakfast may be consumed after fasting plasma glucose draw. BYL719 may be administered 1 hour after breakfast. Patients should fast for 1 hour after the administration of BYL719. Bloodwork results do not need to be resulted prior to dosing on this day (because BYL719 dosing is continuous); however, all bloodwork must be reviewed and the patient contacted within 24 hours (excluding weekends and holidays) if an abnormality is detected which would affect dosing.

- CBC, including WBC (differential not required), Hgb and platelet count
- CMP, including BUN, creatinine and liver function tests
- Magnesium, amylase and lipase
- Fasting glucose
- Tumor markers (CA 15-3 and CEA)
- Plasma collection from 10 ml blood for cfDNA extraction and analysis

10.7.4 EKG will be performed and reviewed on Day 1 +/- 7 days of Cycle 3, Cycle 5, and then every 3rd cycle (Cycle 8, Cycle 11, etc).

10.7.5 PK bloodwork for research purposes (for specified cycles only, see schedule in Section 10.11).

10.7.6 Estradiol will be performed Day 1 +/- 7 days of Cycle 3, Cycle 5, and then every 3rd cycle (Cycle 8, Cycle 11, etc) thereafter, for patients who are receiving pharmacologic ovarian suppression

10.7.7 **Patients who are on study under Amendment 13** will present for one MD visit every other cycle. Patient's will complete all assessments per Section 10.1.

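### The only toxicity summary in Section 14.4, maximum grade over all cycles, rises with time on drug, so the tables cannot fairly inform the daily-versus-intermittent hypothesis if time on drug differs

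*Combined protocol and SAP*

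**What the plan says.** Section 14.4 is the only place in the Biostatistics section that says how the secondary safety objective is summarised. "Selected non-hematologic and hematologic toxicities will be described", "with the maximum grade over all cycles used as the summary measure per patient". It names no common time window, exposure-adjusted rate, time to onset or table of time on drug. Section 2.2 applies the safety objective to Arms A, B, C and D.

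Treatment has no fixed length (Section 9.5): "Patients will continue on treatment until progression of disease or unacceptable toxicity".

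Section 3.8 gives the hypothesis added with the intermittent arms: "We additionally hypothesize that intermittent dosing of BYL719 will allow for dose escalation and treatment with less toxicity than daily BYL719". Section 14 attaches no test, estimate or planned contrast to it.

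Scheduled monitoring thins out with time. From Cycle 3, Section 10.7 sets "One MD clinic visit per cycle". Under Amendment 13, for patients treated for more than 75 weeks, visits move to every other cycle, and so do blood tests (Table 10-1 footnotes): "Patients on study under Amendment 13 will have relevant blood and cfDNA collection every other cycle".

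**The concern.** The worst grade a patient ever has is cumulative: each further cycle can raise it and none can lower it. Two groups with the same risk per cycle but different time on drug will differ on it, and a real difference in risk can be hidden or exaggerated.

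Unequal duration is plausible on the protocol's own rationale. In the phase I study of fulvestrant with a pan-PI3K inhibitor cited in Section 3.7, the longest-lasting benefit was on the intermittent schedule (two patients still on treatment at 15 and 17 months), while a responder on daily dosing withdrew in the setting of grade 3 rash.

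No formal comparison is planned, so the descriptive tables are where a reader will judge the Section 3.8 hypothesis. What is at stake is that reading, not a dose decision.

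**Working it through.** The plan states no rate, sample size or power for this summary, so there is no figure of its own to reproduce. The check has three parts.

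**1. Scheduled monitoring.** Counts per 28-day cycle from Table 10-1 and Sections 10.2 to 10.7:

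| Period | Toxicity assessments | Safety blood tests |
|---|---|---|
| Cycle 1 | 3 by Table 10-1 (Days 1, 8, 15); 2 by the text, since Section 10.3 lists a Day 8 visit without a separate toxicity item | 2 |
| Cycle 2 | 2 | 2 |
| Cycle 3 onward | 1 | 1 |
| Amendment 13 | 0.5 | 0.5 |

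- By Cycle 3, assessments fall 2/1 = 2-fold to 3/1 = 3-fold, and blood tests 2/1 = 2-fold.
- Under Amendment 13, assessments fall 2/0.5 = 4-fold to 3/0.5 = 6-fold, and blood tests 2/0.5 = 4-fold. This starts after 75/4 = 18.75 cycles.
- EKGs thin out sooner. Two per cycle become one every two to three cycles (4- to 6-fold), then one every four cycles under Amendment 13 (8-fold).

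The calendar for these items is the same in all arms.

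**2. Dependence on duration.** Let h be the risk per cycle of a grade 3 or higher event, assumed constant. The share with maximum grade 3 or higher after k cycles is 1 - (1 - h)^k.

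| h (assumed) | 3 cycles | 6 cycles | 12 cycles |
|---|---|---|---|
| 0.03 | 9% | 17% | 31% |
| 0.05 | 1 - 0.95^3 = 14% | 1 - 0.95^6 = 26% | 1 - 0.95^12 = 46% |

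Now suppose that intermittent dosing truly halves the risk, 0.025 against 0.05 per cycle:

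| Cycles, daily / intermittent | Daily | Intermittent |
|---|---|---|
| 4 / 4 | 1 - 0.95^4 = 0.19 | 1 - 0.975^4 = 0.10 |
| 4 / 8 | 0.19 | 1 - 0.975^8 = 0.18 |
| 4 / 12 | 0.19 | 1 - 0.975^12 = 0.26 |

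The benefit disappears at 8 cycles and reverses at 12. A common 4-cycle window keeps 0.19 against 0.10.

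**3. What works the other way.**

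- *Early toxicity.* Assume a Cycle 1 risk of 0.30 (daily) against 0.10 (intermittent), then 0.01 per cycle in both. At 4 cycles each: 1 - 0.70 × 0.99^3 = 0.32 against 1 - 0.90 × 0.99^3 = 0.13, a difference of -0.19. If intermittent patients stay 12 cycles, their share is 1 - 0.90 × 0.99^11 = 0.19 and the difference is -0.13. It shrinks but does not reverse.
- *Detection.* A symptom-free laboratory abnormality lasting 7 days (assumed) is caught by a scheduled draw with probability 7/14 = 0.50, 7/28 = 0.25 or 7/56 = 0.12 at 14-, 28- or 56-day intervals. Late events are therefore more often missed, which offsets part of the rise. Unscheduled checks would raise these figures.

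**The case against.** The strongest reply is that the plan makes no such comparison. The objective is descriptive, the arms are not randomised, and the hypothesis in Section 3.8 has no endpoint attached. This stands: the harm is limited to a descriptive reading.

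The second reply is that a fixed-window measure exists. Section 9.4 defines DLT within Cycle 1 and adds a safety assessment at the end of Cycle 2, and Section 14.3 has DLT and grade 4 rules for the expansion phase. It would therefore be wrong to infer that the trial lacks any toxicity measure over comparable time. But the DLT serves dose-finding. By the specific criteria in Table 9-2, a first grade 3 rash lasting 7 days or less does not count, nor does grade 3 hyperglycemia that resolves to grade 0 within 14 days of starting oral treatment. The Cycle 2 assessment feeds no summary in Section 14.

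The third reply is that toxicity is mostly early. Section 3.7 reports that three of four DLTs were rash, generally arising at days 10-14, and high-grade events lead to interruption, reduction or discontinuation, so a constant risk per cycle is doubtful. This stands for rash. It is weaker for later events: Section 9.4 itself plans for late-appearing toxicity, and Section 3.5.2 notes a tendency to higher exposure after a month at 270 and 400 mg.

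A reader might also infer that intermittent dosing is bound to look more toxic, or that monitoring falls fourfold for everyone. The documents support neither. The text available gives no time on drug by arm (Tables 3-1 and 3-2 were not in it). The fall in assessments and blood tests reaches fourfold only beyond 75 weeks. Longer exposure and sparser monitoring pull in opposite directions.

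**Conclusion.** The point holds in a limited form. Maximum grade over all cycles is the only summary in Section 14.4, and it depends on time on drug. If duration differs between the daily and intermittent arms, the tables cannot fairly inform the Section 3.8 hypothesis.

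The possible size is material for toxicities that keep accruing: at an assumed 5% per cycle, duration alone moves the share from 14% at 3 cycles to 46% at 12. It is smaller for early toxicities such as rash. The net direction is not fixed. All risks, durations and event lengths used here are assumptions.

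No dose decision, stopping rule or primary conclusion is affected. The change is worth making because it is cheap and removes one avoidable distortion.

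**What to change.** In Section 14.4, keep the all-cycle maximum grade and add, by arm and dose level:

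- the maximum grade within Cycles 1-2, a 56-day window with one assessment calendar for all arms, and the number of patients who completed it;
- events per patient-cycle from Cycle 3 onward, with time under Amendment 13 shown separately;
- time on BYL719.

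Base any descriptive statement about daily versus intermittent toxicity on the common-window and exposure-adjusted figures. State beside it that the arms also differ in dose, AI and calendar time, which no window removes. State too that 56 days hold 56 BYL719 dosing days in Arms A and B, 2 × 14 = 28 in Arm C and 2 × 20 = 40 in Arm D.

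The cost is SAP wording and a few table columns. Section 10.10 already records start and end dates for each adverse event, so closed accrual is no obstacle. The downside is that late-onset toxicity sits outside the common-window table, although it still appears per patient-cycle and in the all-cycle maximum.

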14.5 Exploratory Objectives

Correlative studies examining patient and clinical factors correlated with BYL719 sensitivity will be done using next generation sequencing and fine copy number analysis of pre-treatment biopsies, as well as proteomic analysis of pre-treatment and on-treatment biopsies. cfDNA analysis in plasma obtained at baseline, Cycle 1 day 1, Cycle 1 day 8, Cycle 1 day 15 and at each subsequent treatment cycle will be performed to assess for a correlation between mutant allele quantification and response to BYL719. We feel that combining the letrozole and exemestane arms for these exploratory analyses is reasonable given their similar mechanisms of action at the level of the breast cancer cell. The correlative studies will be primarily descriptive and provide the preliminary evidence necessary to recommend BYL719 and specific biomarkers for future clinical study.

cfDNA extraction from 2-6 ml plasma obtained at the time of routine blood draws has been feasible in patients with metastatic breast cancer according to ongoing study, MSKCC IRB #13-050, [name] – PI. DNA quantity and integrity is assessed by qPCR and uniformly has yielded amplifiable fragments suitable for dPCR and small amplicon library construction. We anticipate that this approach will be informative for patients with tumors harboring a *PIK3CA* mutation and exploratory for patients whose tumors harbor potential driver mutations for which additional dPCR assays will be designed ([Dawson, Tsui et al. 2013](#)).

The protocol consent form asks participants for permission to discuss their research findings if their samples are used in an HBUC or Biospecimen project and an incidental finding is made that may be critical to their preventative care. If a participant agrees to be contacted, the participant will not be told the specific results of the research test, but will be informed that their samples were used in a project and a potential risk was uncovered. If the participant is interested in further discussion of the research findings, the participant will be

asked to come into MSKCC Clinical Genetics Service for counseling and specific genetic testing.

Based on our ongoing experience with our tumor biopsy study to evaluate molecular mechanisms of resistance in patients with HER2+ disease (MSKCC IRB # 06-163, [name] - PI), we anticipate that it will be feasible to obtain a pre-treatment biopsy in at least 80% of patients (~30 patients assuming total accrual of 38 patients). Due to logistical issues, such as lack of sufficient viable cells in the biopsy sample, it is possible that a viable pre-treatment biopsy sample may not be obtained in several patients.

In order to determine if pharmacodynamic markers of PI3K pathway hyperactivation and inhibition predict for PFS, proteomic analysis of pre-treatment and Day 15 on-treatment biopsies will be performed. The Spearman's rank correlation of inpatient percent change in PI3K pathway activation signature (measured as a continuous variable) with percent tumor volume change at 8 week CT scan (measured as a continuous variable) will be calculated to evaluate whether pharmacodynamic markers of PI3K pathway inhibition are predictive of response to therapy.

We anticipate that it will be feasible to obtain a Day 15 on-treatment biopsy in at least 50% of patients (~19 patients assuming total accrual of 38 patients).

To evaluate mechanisms of AI resistance, the analysis will include pre-treatment tumor biopsies obtained in patients who had POD on an AI at the time of study consent, on-treatment biopsies, as well as optional post-progression biopsies. We estimate that this will include about half of patients in the dose-finding phase (because those with stable disease will be excluded), and all patients in the expansion phase who have a viable pre-treatment biopsy sample.

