2.3 Exploratory Objectives

- Arms A, B, C and D: To evaluate mechanisms of AI resistance and predictors of BYL719 sensitivity through next generation sequencing and fine copy number analysis of a pre-treatment biopsy

- Arms A, B, C and D: To evaluate predictive and pharmacodynamic markers of PI3K pathway inhibition with BYL719 through proteomic analysis of pre-treatment and on-treatment biopsies
- Arms A, B, C and D: To evaluate cell free DNA (cfDNA) as a predictive biomarker of PI3K pathway inhibition with BYL719 through the sequential quantification of *PIK3CA* mutant alleles by digital PCR (dPCR) on serial plasma collections.
- Arms A, B, C and D: To evaluate mechanisms of acquired resistance with correlative studies of on-treatment and optional post-progression tumor biopsies

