analysis to identify determinants of sensitivity. In order to understand the action of BYL719 on HR+ breast cancer treated with an AI, we will also evaluate a Day 15 on-treatment biopsy for pharmacodynamic markers of pathway inhibition which correlate with improved PFS.

[figure not shown]
If this study is successful, these results may lead to further study of this non-chemotherapy combination, supported by science from MSKCC labs and Novartis, ultimately moving towards our goal of delaying or preventing resistance to endocrine therapy in the treatment of HR+ breast cancer.

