In order to determine if pharmacodynamic markers of PI3K pathway hyperactivation and inhibition (e.g. P-AKT, P-S6, P-4EBP) predict for PFS, we will also perform proteomic analysis of pre-treatment and on-treatment biopsies. When possible, Day 15 on-treatment biopsies should be performed from the same tumor site as the pre-treatment biopsies. The levels of pathway protein expression and their activation will be determined by Collaborative Enzyme Enhanced Reactive-immunoassay (CEER, Promethius Biosciences). CEER can be performed in a multiplexed fashion directly on clinical samples that may be available in limited amounts. This phosphoproteomic assay utilizes the formation of unique immuno-complexes between capture antibodies (Abs) printed on a nitrocellulose microarray surface, the target molecule (in cell lysate reacted with the slide), and two independent detector-Abs. One of the detector-Abs is conjugated to glucose oxidase (GO), and the other is conjugated to Horse Radish Peroxidase (HRP). Target detection requires the presence of both detector-Abs and the enzyme channeling event between GO and HRP will not occur unless both Abs are in close proximity. Using this assay, receptor tyrosine kinases and downstream pathway proteins can be detected at the single cell level (sensitivity of about 100 zeptomoles). Inpatient percent change in quantitative PI3K pathway activation signature will be scored and compared to percent tumor volume change at 8 week CT scan. The Spearman's rank correlation of inpatient percent change in PI3K pathway activation signature (measured as a continuous variable) with percent tumor volume change at 8 week CT scan (measured as a continuous variable) will be calculated to evaluate whether pharmacodynamic markers of PI3K pathway inhibition are predictive of response to therapy. We will also perform immunohistochemistry on a paraffin block to evaluate for PTEN loss. This may be performed on archival primary tumor block or archival metastatic tumor if not enough tumor is available from the pre-treatment metastatic biopsy. PTEN will be scored as 0 (PTEN loss), 1 or 2, as previously described for breast cancer tissue by [name] at MSKCC¹⁴. Specifically, the cytoplasmic and/or nuclear immunoreaction will be scored based on intensity whereby a score of 2 = positive (equal in intensity to normal epithelial cells), a score of 1 = weak (reduced intensity as compared with normal epithelial cells), and a score of 0 = negative (no immunoreaction).¹⁵

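### The pathway-marker analysis is meant to show whether markers predict PFS, but the only statistic specified uses 8-week tumor volume change and so addresses response

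*Combined protocol and SAP*

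**What the plan says.** Three sections name PFS as the outcome of interest for the pharmacodynamic markers. Section 3.8 says the Day 15 biopsy will be examined for "pharmacodynamic markers of pathway inhibition which correlate with improved PFS". Section 10.12 opens its proteomic plan with "In order to determine if pharmacodynamic markers of PI3K pathway hyperactivation and inhibition (e.g. P-AKT, P-S6, P-4EBP) predict for PFS", and Section 14.5 repeats this almost word for word: "In order to determine if pharmacodynamic markers of PI3K pathway hyperactivation and inhibition predict for PFS".

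In both 10.12 and 14.5 the statistic that follows is a Spearman rank correlation of the patient's percent change in the pathway signature "with percent tumor volume change at 8 week CT scan (measured as a continuous variable"). Its declared purpose is "to evaluate whether pharmacodynamic markers of PI3K pathway inhibition are predictive of response to therapy".

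The formal objective in Section 2.3 is broader and names no clinical endpoint: "To evaluate predictive and pharmacodynamic markers of PI3K pathway inhibition with BYL719 through proteomic analysis of pre-treatment and on-treatment biopsies".

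Elsewhere, PFS is handled by Kaplan-Meier methods, arm by arm and in the expansion cohort only (Sections 12.1 and 14.4), with no marker or other covariate. Sections 1.0 and 4.0 add that efficacy in Arms A and B will be estimated from the dose-escalation patients, because those arms have no expansion cohort.

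Section 14.5 describes the correlative work as mainly descriptive, combines the letrozole and exemestane arms for it, and expects a Day 15 biopsy in at least half of 38 patients, about 19.

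**The concern.** The question moves from PFS to response within a single paragraph. Someone who carried out Section 14.5 exactly as written would report a correlation with early tumor shrinkage and would have nothing to say about PFS.

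Week-8 volume change is also an incomplete substitute. It has no value for a patient with no measurable lesion, it takes no account of new lesions, and it may be missing for a patient who stops before the scan. Patients who progress early are informative about resistance, and Section 14.5 gives no rule for them.

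Section 14.5 expects these studies to supply preliminary evidence for recommending biomarkers for later trials. If no marker-PFS analysis is specified, any such result will be post hoc, with population, time origin and cut-point chosen after the data are seen.

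**Working it through.** **1. Aim against method.**

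| Section | Outcome named in the aim | Statistic specified |
|---|---|---|
| 2.3 | none | none |
| 3.8 | PFS | none |
| 10.12 | PFS | Spearman with 8-week volume change, to judge response |
| 14.5 | PFS | the same |
| 12.1, 14.4 | PFS (no marker) | Kaplan-Meier by arm, expansion cohort |

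No Cox model, log-rank comparison, landmark analysis or other link between a marker and PFS appears anywhere.

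**2. The plan's own figure.** 0.50 × 38 = 19.0, which reproduces the expected 19 or so Day 15 biopsies. This is a planning figure. It assumes that each patient also has a usable pre-treatment sample, and Section 1.0 reports that accrual closed at 51.

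**3. Who may lack a volume-change value.** Section 6.2.10 admits patients with non-measurable disease. Section 10.12 excludes bone-only patients from the Day 15 biopsy, so that group is already outside the 19 and could not enter a marker-change analysis of any outcome. Section 10.9 requires a disease evaluation at the end of treatment if none was done in the previous 28 days, so some patients who stop early will have imaging; the plan does not say whether that scan stands in for the 8-week CT. The documents give no count for either kind of loss.

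**4. What such losses would do to the Spearman analysis.** The plan states no alpha, power or effect size here, so two-sided 5% and 80% power are assumed. With Fisher's z and Spearman variance 1.06/(n − 3), the detectable correlation is tanh[(1.960 + 0.842) × √(1.06/(n − 3))].

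- n = 19: √(1.06/16) = 0.257; tanh(0.721) = .62
- n = 15 (assumed): √(1.06/12) = 0.297; tanh(0.833) = .68
- n = 10 (assumed): √(1.06/7) = 0.389; tanh(1.090) = .80

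Even with all 19 pairs, an observed correlation of .40 would have a 95% interval of about −.08 to .73.

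**5. What an added PFS analysis could show.** For a continuous covariate in a Cox model, the number of events needed is (1.960 + 0.842)² / (log HR per SD)², so the detectable HR is exp(2.802/√events).

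- 19 events (every patient with paired biopsies progresses or dies): exp(0.643) = 1.90
- 15 events: exp(0.723) = 2.06
- 10 events: exp(0.886) = 2.43

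Ten is the most that could arise if PFS came only from the 20 Arm C and D expansion patients at the planned 50% biopsy yield (0.50 × 20 = 10). The population must therefore be stated.

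**The case against.** The strongest reply is that a reader might infer that a formal objective goes unanalysed, and the documents do not support that. Section 2.3 speaks only of predictive and pharmacodynamic markers, and a correlation with tumor shrinkage serves that wording. PFS enters through the rationale and through the introductory clauses of 10.12 and 14.5. On this view, replacing PFS with response in those clauses would remove the inconsistency without a new model. That is correct as a minimum repair. It leaves unasked the question that three sections pose.

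A second reply is that the work is exploratory and mainly descriptive, in a phase I trial whose primary objective is a dose. That limits the weight of the point, but a descriptive purpose does not supply a marker-PFS analysis, and the method that is specified has a different target.

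A third concerns the argument from missing values. A reader might infer that a particular share of pairs, such as a third, will be lost from the Spearman analysis while a PFS analysis keeps all 19. The documents support neither half. They give no rate of loss, bone-only patients have no Day 15 biopsy and so contribute to neither analysis, and PFS in Arms C and D is currently planned in the expansion cohort only. Precision for PFS also depends on events, not patients, so no gain in power over the Spearman test is shown.

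Finally, stratifying a model of about 19 patients by arm would leave few events per stratum and would cut across the pooling that Section 14.5 chooses deliberately. That objection stands, and the remedy below respects it.

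**Conclusion.** The point holds as a mismatch inside Sections 10.12 and 14.5, and with the rationale in 3.8: the stated aim is PFS, the specified statistic concerns response, and no marker-PFS analysis is planned. Its importance is low. The formal objective names no endpoint, the analysis is exploratory, and neither the recommended phase II dose nor the secondary endpoints are affected.

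The incompleteness of 8-week volume change is a supporting reason of unknown size. The range .68 to .80 for the detectable correlation rests on assumed losses to 15 or 10 pairs, and on 80% power and two-sided 5%, none of which the plan states. The case for a PFS analysis is that it answers the question asked; it would not be more precise.

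**What to change.** In Sections 14.5 and 10.12:

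- Add a descriptive Cox model (or a concordance index) for PFS, with percent change in the pathway signature as a continuous covariate. Start time at the actual date of the on-treatment biopsy, since the timing of that biopsy is left to the investigators.
- Pool the letrozole and exemestane arms, as Section 14.5 already states, and stratify at most by continuous versus intermittent schedule. Report an estimate with a confidence interval.
- State that, for this purpose, PFS is derived for every patient with paired biopsies, including dose-finding patients. The scheduled disease evaluations in Section 10.9 apply to all arms, so the data are already collected.
- Keep the Spearman correlation and label it as the response analysis.

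If the team does not want a PFS analysis, the minimum is to reword the aim in Sections 3.8, 10.12 and 14.5 as tumor response.

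The cost is one extra exploratory analysis on existing data, with no further patient procedures. Its drawback is low precision: a detectable hazard ratio of about 1.9 per SD with 19 events and 2.4 with 10, under the assumptions above.
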